## 474           **12. Other Tabulations**

475

476           Individual listings for each participant will include the following:

477           • Treatment group, age, gender, race/ethnicity, duration, height, weight, and BMI  
478           • Study related information (like enrollment and randomization dates, enrollment and  
479           randomization HbA1c, randomization C-peptide, status, run-in requirement)

480           • Previous insulin method, CGM, SMBG, non-insulin medications, device months used  
481            and manufacturer

482           • Past SH and DKA events

483           • Physical exam results

484           • Income, education, and insurance

485           • Pre-existing medical conditions other than diabetes

486           • Medication at enrollment

487           • Baseline glucose metrics

488

489 The following tabulations and analyses will be performed by treatment group:

490           • Sensor performance metrics (difference, absolute relative difference, and  
491            International Organization for Standardization criteria)

492           • % time CGM data available - overall and by month

493

494 The following tabulations and analyses will be performed by treatment group to assess  
495 intervention adherence for the study:

496           • Sensor use – hours per week and percent time of use – overall and by month

497           • The daily frequency of downloaded BGM use - overall and by month

498

499 The following tabulations will be performed for the CLC arm only:

500           • Performance metrics, describing the Control-IQ system and its components like:

501            ○ % time CGM data were available to the Control-IQ system – overall and by  
502            month

503            ○ % time in different operational modes - overall and by month

504            ○ Rate of different failure events and alarms per 24 hours recorded by the  
505            Control-IQ system – overall and by month

506           • Technology Expectations Survey score at baseline and Technology Acceptance  
507            Survey score at 26 weeks

508

509

### 510           **13. Planned Interim Analyses**

511

512 No formal interim analyses are planned for this study.

513

514 The DSMB will review safety data collected for the study. The data to be reviewed will include  
515 information regarding all of the following:

516           • Status of randomized participants

517           • Recruitment rates by month and by site  
518           • Baseline demographic and clinical characteristics  
519           • Dropped participants and reasons for discontinuing  
520           • Protocol deviations  
521           • Device issues  
522           • Scheduled and unscheduled visits and contacts  
523           • Frequency of CGM and system use over time and by site  
524           • Reportable adverse events as described in section 8 of the protocol  
525           • CGM-based hypo- and hyper-glycemic events during the 2-week baseline and all  
526           available post randomization data

527  
528       The DSMB will review safety data at intervals, with no formal stopping rules other than the  
529       guidelines provided in the participant-level and study-level stopping criteria (as defined in the  
530       protocol).

531

## 532       **14. Subgroup Analyses**

533

534       In exploratory analyses, all primary outcomes found significant according to the hierarchical  
535       rules outlined above will be assessed separately in various subgroups and for continuous  
536       variables according to the baseline value as defined below. Tests for interaction with treatment  
537       group will be performed and further explored if an interaction will be found in the first place.

538       Interpretation of subgroup analyses will be viewed with caution, particularly in the absence of an  
539       overall significant difference a. For continuous variables, results will be displayed in subgroups  
540       based on cutpoints although the analysis will utilize the variable as continuous, except for age  
541       which will be analyzed both as a continuous variable and in two age groups. If there is  
542       insufficient sample size in a given subgroup, the cutpoints for continuous measures may be  
543       adjusted per the observed distribution of values. Cutpoint selection for display purposes will be  
544       made masked to the outcome data and generally based on means or medians.

545           • Baseline HbA1c  
546           • Baseline CGM time spent <70 mg/dL  
547           • Baseline CGM time spent >180 mg/dL  
548           • Baseline CGM time 70-180 mg/dL  
549           • Device use before the enrollment: pump/MDI, CGM/no CGM, and combinations of  
550           both  
551           • Age (<25 vs.  $\geq$ 25)  
552           • Sex  
553           • Race

554           • Clinical site  
555           • Body mass index  
556           • Income, education, and/or insurance status  
557           • Baseline scores for quality of life, hypoglycemia awareness and fear questionnaires  
558           • C-peptide level

559  
560  
561           **15. Multiple Comparison/Multiplicity**

562           Primary Analysis

564           Since there will be a single comparison for the primary outcome (CGM-measured % 70-180  
565           mg/dL), no adjustment is needed.

566  
567           Secondary Hierarchical Analyses

568           The hierarchical testing procedure described above in Section 7.1 will be used to control the  
569           overall type 1 error for the primary outcome plus five key secondary outcomes identified above.

570  
571           All Other Secondary Analyses

572           For comparison of other efficacy endpoints considered exploratory, the false discovery rate  
573           (FDR) will be calculated using the Benjamini-Hochberg method adapted using the two-stage  
574           test. FDR adjusted p-values will be calculated separately for the following categories:

575           • CGM metrics over 24hr  
576           • CGM metrics during awake periods  
577           • CGM metrics during nighttime periods  
578           • CGM metrics during the first three months  
579           • HbA1c analyses  
580           • Insulin, weight, BMI  
581           • Questionnaires  
582           • Subgroup analyses (separately for each primary and secondary hierarchical outcomes  
583           found significant)

584  
585  
586           P-values from safety analyses, sensitivity analyses and per-protocol analyses will not be adjusted  
587           for multiple comparisons.

590                   **16. Exploratory analyses**

591

592   No p-values will be calculated for these analyses.

593

594   The following metrics will be reported with the appropriate statistics by the associated CL mode:

595                   • % below 70 mg/dL

596                   • % above 180 mg/dL

597                   • % time in range 70-180 mg/dL

598                   • mean glucose

599                   • coefficient of variation

600

601

602                   **17. Additional Tabulations and Analyses**

603

- 604                  • 24 hours profiles with mean (or medians) and quartiles lines and 4-week interval boxplots  
605                  by treatment arms for:

606                    ○ % below 70 mg/dL

607                    ○ % above 180 mg/dL

608                    ○ % time in range 70-180 mg/dL

609                    ○ mean glucose

610                    ○ coefficient of variation

- 611                  • Subjects in the CLC arm will enter their bedtimes in the system. Summary statistics for  
612                  the same outcome metrics listed in the previous bullet will be given stratified by sleep and  
613                  awake times.

- 614                  • It is expected to collect most of the continuous insulin data in the two treatment groups  
615                  over 26 weeks. The two insulin analyses (total daily insulin per kg and basal: bolus insulin  
616                  ratio based on the subject-reported values) will be repeated using 2 weeks of system  
617                  and/or pump data at 2, 13, and 26 weeks.

# The International Diabetes Closed Loop Protocol 3 (DCLP3) Trial: Pivotal Trial of t:slim X2 with Control-IQ Technology

## **Addendum to Statistical Analyses Plan Version 1.0:**

DCLP3 SAP V1.0  
10\_12\_2018.pdf

May 8, 2019

30  
31  
32  
33  
34  
35  
36  
37  
38  
39

[name]  
I am the author of this document  
**Lead Statistician and Author:** 2019-05-08 12:16:04:00

---

40  
41  
42  
43  
44  
45  
46  
47  
48  
49  
50  
51  
52  
53  
54

**Senior Statistician Approver:** \_\_\_\_\_

[name]  
I am approving this document  
2019-05-08 16:34-04:00

---

55

56

57

58 1. On January 31, 2019 it was found out that most insulin summary metrics displayed in  
59 t:connect for the Control-IQ study pump are not correct.

60 For the CLC group, since some sites used this incorrect information to record insulin data on  
61 CRF forms at 2, 13, and 26 weeks, the insulin information entered on the CRF forms for the  
62 CLC group will not be used in any analyses. The 2 weeks of actual insulin data uploaded from  
63 the pump at 2, 13, and 26 weeks will be used instead.

64 For the SAP group, the CRF data will be used.

65 The above insulin analyses will replace the ones mentioned in sections 7.4 and 17 of the  
66 Statistical Plan.

67

68

69 2. In section “5.4 Analyses Windows”, it was implied that BMI (height and weight) will be  
70 collected at 2, 13, and 26 weeks. Because there is no collection of height and weight at 13 weeks,  
71 the analyses mentioned in section “7.5. Weight and Body Mass Index Analyses” will not include  
72 the 13-week time point.

73

74 3. In section “4.3 Calculation of CGM Metrics” it was stated that: “*If an enrolled subject can*  
75 *show CGM use at least 11 out of the 14 days prior to enrollment, then he/she can proceed*  
76 *directly to randomization*”. Since screening and the associated CGM use assessment may occur  
77 later than the enrollment date in some cases, the above sentence will be changed to: “*If an*  
78 *enrolled subject can show CGM use at least 11 out of the 14 days prior to screening, then he/she*  
79 *can proceed directly to randomization*”

80

81 4. On March 4, 2019 the Closed-Loop feature was suspended studywide due to an Unanticipated  
82 Problem with the Closed-Loop feature delivering insulin when not needed; the Closed-Loop  
83 feature was resumed on March 29, 2009.

84 All primary and secondary analyses described in the SAP will continue to be conducted  
85 according to the intent-to-treat principle and will not exclude any data during this suspension  
86 period.

87

88 New sensitivity analyses will be added for the primary, secondary hierarchical CGM outcomes,  
89 and for % time in different operational mode outcomes that will exclude data during the above-  
90 mentioned suspension period.

91

92 5. On lines 285-288 we wrote: “*Residual values will be examined for an approximate normal*  
93 *distribution. If residuals are highly skewed even after the transformation, then a transformation*  
f:\user\diabetes studies\nih-uc4\idcl\dclp3 trial master file\statistical analyses\electronic data closeout  
binder\2.sap\dclp3 sap addendum 5\_8\_2019.docx Last Printed: 5/8/2019 12:16:09 PM Page 3 of 4

94 *or robust statistical method (e.g., non-parametric or MM estimation) will be used instead.” Typo*  
95 *- “even after the transformation” does not belong in the sentence and will be removed from the*  
96 *final draft. Here is the final version: “Residual values will be examined for an approximate*  
97 *normal distribution. If residuals are highly skewed, then a transformation or robust statistical*  
98 *method (e.g., non-parametric or MM estimation) will be used instead.”*

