### 92     4.2. Secondary Efficacy Endpoints

93

94     4.2.1. Hierarchical Endpoints

95     The following secondary endpoints will be tested in a hierarchical fashion as described in  
96     section 7.1 below.

- 97       • CGM-measured % above 180 mg/dL over 26 weeks
- 98       • CGM-measured mean glucose over 26 weeks
- 99       • HbA1c at 26 weeks
- 100       • CGM-measured % below 70 mg/dL over 26 weeks
- 101       • CGM-measured % below 54 mg/dL over 26 weeks

102

103 **4.2.2. Other Secondary Endpoints**

104

105 The following endpoints are considered exploratory.

- 106     • CGM metrics related to overall control over 26 weeks
  - 107         ○ % in range 70-140 mg/dL
  - 108         ○ glucose variability measured with the coefficient of variation
  - 109         ○ glucose variability measured with the standard deviation
- 110     • CGM metrics related to hypoglycemia over 26 weeks
  - 111         ○ % <60 mg/dL
  - 112         ○ low blood glucose index
  - 113         ○ hypoglycemia events (defined as at least 15 consecutive minutes <70 mg/dL)
- 114     • CGM metrics related to hyperglycemia over 26 weeks
  - 115         ○ % >250 mg/dL
  - 116         ○ % >300 mg/dL
  - 117         ○ high blood glucose index
- 118     • CGM metrics by time of day
  - 119         ○ Calculate all CGM metrics listed above (including the primary outcome) for:
  - 120         ○ All 24 hours of the day (primary analysis for time in range)
  - 121         ○ Daytime only (06:00AM to 00:00AM)
  - 122         ○ Nighttime only (00:00AM to 06:00AM)
- 123     • CGM metrics for the first three months post-randomization
- 124     • HbA1c at 26 weeks
  - 125         ○ HbA1c <7.0%
  - 126         ○ HbA1c <7.5%
  - 127         ○ HbA1c improvement from baseline >0.5%
  - 128         ○ HbA1c improvement from baseline >1.0%
  - 129         ○ HbA1c relative improvement from >10%
  - 130         ○ HbA1c improvement from baseline >1.0% or HbA1c <7.0%
- 131     • Insulin at 26 weeks
  - 132         ○ Total daily insulin (units/kg)
  - 133         ○ Basal: bolus insulin ratio
- 134     • Weight and body mass index at 26 weeks
- 135     • Fear of Hypoglycemia Survey (HFS-II) at 26 weeks – total score and 3 subscales:
  - 136         ○ Behavior (avoid)
  - 137         ○ Behavior (maintain high BG)
  - 138         ○ Worry
- 139     • Hyperglycemia Avoidance Scale at 26 weeks – total score and 4 subscales:
  - 140         ○ Immediate action
  - 141         ○ Worry

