### 329 **7.1.2 HbA1c**

330 For the HbA1c analysis, a longitudinal model the primary analyses will be fit using values at  
331 baseline, 13 and 26 weeks adjusting for age, prior CGM use and pump use as fixed effects and  
332 site as a random effect. Missing data will be handled by direct likelihood in this longitudinal  
333 model. This model implicitly adjusts for baseline HbA1c by forcing the treatment groups to have  
334 the same mean value at baseline. Local HbA1c values measured at the site will be included as an  
335 auxiliary variable (analogous to imputing any missing lab values). The p-value used in the  
336 hierarchical analysis above will be based on the laboratory values at 26 weeks. Regression  
337 diagnostics will be employed analogous to as described in Section 6 for the primary outcome.

338

339 **7.2. Other CGM Secondary Analyses**

340

341 The analyses for the other secondary CGM-measured outcomes will parallel those mentioned  
342 above for the primary outcome. These will be done using CGM data over the entire 6 months of  
343 follow-up and repeated restricting to the first 3 months of follow-up (see Section 4.3).

344

345 **7.3. HbA1c Analyses**

346

347 The analysis of HbA1c as a continuous outcome at 26 weeks is described above in Section 7.1.2.  
348 A similar treatment arm comparison will also be done at 13 weeks. Summary statistics will be  
349 given by treatment arm at 13 and 26 weeks.

350 For the binary HbA1c outcomes listed in Section 4, risk-adjusted percentages by treatment group  
351 will be computed at 26 weeks from a logistic regression model. The logistic regression will  
352 adjust for baseline HbA1c, age, prior CGM and pump use as fixed effects, and clinical site as a  
353 random effect.

354

355 **7.4. Insulin Analyses**

356

357 Summary statistics appropriate to the distribution for total daily insulin and the bolus:basal ratio  
358 will be given by treatment group at 2, 13 and 26 weeks. A longitudinal regression model will be  
359 fit for both of these metrics using direct likelihood. A point estimate and confidence interval will  
360 be given for the treatment arm difference at 13 and 26 weeks. Regression diagnostics will be as  
361 described above for the primary outcome.

362

363 **7.5. Weight and Body Mass Index Analyses**

364

365 Summary statistics appropriate to the distribution for weight and BMI will be given by treatment  

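### The SAP addendum takes insulin outcomes from pump uploads in the CLC arm and from CRFs in the control arm, and removes the only comparison that used the same kind of source in both

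*SAP*

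**What the plan says.** Below, CLC is the closed-loop arm, the control arm is the sensor-augmented-pump group, and SAP means the analysis plan.

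- **SAP 4.2.2** lists total daily insulin (units/kg) and basal:bolus ratio at 26 weeks among the other secondary endpoints, and says of that list: "The following endpoints are considered exploratory".
- **SAP 7.4** fits a longitudinal model to each. A point estimate and confidence interval will "be given for the treatment arm difference at 13 and 26 weeks". It names no covariates. Protocol 10.7 and 10.7.2 do: the baseline value of the metric, age, prior CGM and pump use, and site.
- **SAP 15** places insulin in a false-discovery-rate category headed "Insulin, weight, BMI" and leaves sensitivity p-values unadjusted.
- **SAP 17** describes these analyses as using values reported by the subject. It plans to repeat them on two weeks of system or pump data at 2, 13 and 26 weeks, and expects most such data to be available in both groups.
- **Addendum item 1** reports that most insulin summaries shown in "t:connect for the Control-IQ study pump are not correct" and that "some sites used this incorrect information to record insulin data on" CRFs. CLC CRF insulin values are therefore barred from every analysis. "The 2 weeks of actual insulin data uploaded from" the pump take their place. For the control arm: "For the SAP group, the CRF data will be used". It adds: "The above insulin analyses will replace the ones mentioned in sections 7.4 and 17 of the" SAP.
- **Protocol 5.3.1.1** specifies download of the study system or personal pump at follow-up visits in both groups.

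**The concern.** Discarding the CLC CRF values is justified. The difficulty lies in what replaces them. SAP version 1.0 had two insulin comparisons, one on reported values and one on device data, each using one kind of source in both arms. The addendum leaves a single comparison in which source and arm coincide.

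A CRF-v-CRF comparison is ruled out because the CLC CRF data may not be used. An upload-v-upload comparison was the section 17 repeat, which is replaced. No other section plans one. The stated reason does not extend that far: the fault is in summaries for the Control-IQ pump, and nothing is said against uploaded pump data from the control arm.

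How much insulin an automated system delivers is a natural question in a device trial. An estimate with a confidence interval and an adjusted p-value will be read as the effect of the device. If CRF and uploaded values differ systematically, part or all of that estimate could reflect the source, and no planned analysis would show it.

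**Working it through.** **1. Which comparisons survive**

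| Comparison | SAP 1.0 | After addendum item 1 |
|---|---|---|
| CRF v CRF | Section 7.4 | Barred (CLC CRF data unusable) |
| Upload v upload | Section 17 | Replaced |
| CLC upload v control CRF | Not planned | The only analysis |

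If control-arm CRF values differ from that arm's uploads by an average b, the estimated arm difference shifts by b in absolute size.

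**2. Inputs.** The documents give no figure for b. The only related figure is the minimum total of 123 for the primary outcome, which reproduces: control n = 1.5 × (1.960 + 1.282)² × (12/7.5)² = 40.35, so 41, with 82 in CLC. Nothing below depends on it. From SAP section 3 I take 168 randomized at 2:1, that is 112 v 56. The offsets are assumptions, in SD units.

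**3. Nominal error with no true effect.** SE = √(1/112 + 1/56) = 0.164 SD. P(p<0.05) = Φ(b/SE − 1.96) + Φ(−b/SE − 1.96). With 100 v 50 (the 150 completers in the protocol's goal), SE = 0.173.

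**4. Under SAP 15.** Two-stage Benjamini-Hochberg at 5%, 400,000 simulated trials, with an assumed family of four independent tests, one of them shifted. A larger family would lower these figures.

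| Assumed offset b | Nominal, 112 v 56 | Nominal, 100 v 50 | After FDR, 112 v 56 |
|---|---|---|---|
| 0 | 5.0% | 5.0% | 1.3% |
| 0.05 SD | 6.1% | 6.0% | 1.8% |
| 0.1 SD | 9.4% | 8.9% | 3.2% |
| 0.2 SD | 23.1% | 21.1% | 10.3% |
| 0.3 SD | 45.0% | 41.0% | 25.6% |

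**5. Precision of an upload comparison.** The number of control-arm uploads is unknown, so two levels are assumed.
- 75% (42): SE = √(1/112 + 1/42) = 0.181, an interval 11% wider than with all 56.
- 50% (28): SE = √(1/112 + 1/28) = 0.211, an interval 29% wider.

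**6. What a within-arm CRF-minus-upload difference can show.** With an assumed CRF-upload correlation r, the 95% half-width is t × √(2(1−r))/√n.
- n = 42, r = 0.9: 2.02 × 0.447/√42 = 0.14 SD.
- n = 28, r = 0.8: 2.05 × 0.632/√28 = 0.25 SD.

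At the wider end it could not exclude a 0.2 SD offset. It describes the gap and does not prove its absence.

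**7. Selection.** Suppose injection (MDI) users are at the protocol's minimum goal, 30 of 150 or 20%, and uploads are missing only among personal-pump users. The control arm then has 56 × 0.20 = 11.2 former injection users. They form 11.2/42 = 27% or 11.2/28 = 40% of its upload set, against 20% in CLC. This is why the upload comparison needs covariate adjustment and should remain a sensitivity analysis.

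**The case against.** Several points on the other side have force.

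- **The stakes are low.** Both endpoints are labelled exploratory. This stands and sets the weight of the point.
- **No bias is shown.** A reader might infer that the planned insulin comparison is biased, or that control-arm CRF values are self-reports being set against device records. The documents support neither. Section 17 does call the values subject-reported, but the addendum shows that some sites filled CLC CRFs from pump software. Control-arm CRF values may also be device-derived, in which case the gap could be small.
- **The nominal error rates overstate the matter.** The plan applies a false-discovery-rate adjustment, and the adjusted figures are the relevant ones for significance claims. This stands. The shift in the estimate and its interval is the same either way.
- **Uploads on both sides are not a perfect match.** CLC participants use one study pump, while control participants may use a personal or a study pump. Pump type would still partly align with arm, so an upload comparison removes the CRF-upload difference but not every device difference.
- **Control-arm pump data may be thin.** Protocol 5.2.1 and 5.2.3 ask control participants to upload CGM data. Pump download rests on 5.3.1.1 and, less clearly for week 2, on section 3.2 and Table 1. The expectation in section 17 predates the addendum. This limits what can be recovered, but the addendum does not say the data were unavailable.

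The remaining point is narrow: the plan once held a check on data source, and the addendum removes it without giving a reason that applies to the control arm.

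**Conclusion.** The point holds, and it is minor. For two exploratory endpoints, data source coincides with arm and no remaining analysis could detect a source effect. An assumed offset of 0.05 SD hardly matters. At 0.2 SD, a false significant result would occur in about 23% of trials nominally, or about 10% after the planned adjustment, against 5% and 1.3% with no offset. These figures rest on 112 v 56 participants, no true effect, offsets chosen for illustration and, for the adjusted ones, a family of four independent tests.

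A reader might go further and doubt the trial's main results or the decision to drop the CLC CRF values. Neither follows: the primary, hierarchical and safety results do not use these data, and the exclusion answers a documented software fault.

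**What to change.** Amend addendum item 1 so that it does not delete the section 17 repeat.

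1. Keep the mixed-source analysis. Add, as a sensitivity analysis only, the arm comparison on two weeks of uploaded pump data in both arms at 13 and 26 weeks, and at week 2 where control-arm pump downloads exist. Do not fill control-arm gaps from CRFs. Adjust for the Protocol 10.7 and 10.7.2 covariates: age, prior CGM and pump use, site, and the baseline insulin metric where it was collected, stating so if it was not. Use the same stated weight for units/kg in both arms. Reconcile addendum item 2, which says weight is not collected at 13 weeks, with Protocol 5.3.1.1, which specifies it.
2. Report how many participants have uploads in each arm, by prior pump use and by study or personal pump, and note that pump type may still partly align with arm.
3. Report the CRF-minus-upload difference with its 95% interval in control participants who have both, as description.
4. Label the data source by arm in every insulin table.
5. Show the two estimates and intervals side by side. If they differ materially in either direction, state that the insulin difference may reflect data source. Do not require both to be significant. For a true 0.5 SD effect masked by an opposite 0.2 SD offset, the mixed analysis sees a net 0.3 SD, so joint significance could occur in at most 45% of trials. The upload comparison alone would detect the effect in 79% (42 uploads) or 66% (28).

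**Cost:** addendum wording, plus processing of control-arm pump downloads already specified at follow-up visits, to the extent they were obtained. The upload interval would be about 11% to 29% wider if 75% to 50% of the control arm have uploads. Because SAP 15 leaves sensitivity p-values unadjusted, the false-discovery-rate family does not change.
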